## STUDY SYNOPSIS

PROTOCOL TITLE	A Phase I/II, Open Label, Study to Assess the Safety and Tolerability of VM202 in Subjects with Amyotrophic Lateral Sclerosis
STUDY PHASE	I/II
INVESTIGATIONAL AGENT	VM202
DOSE	64 mg of VM202
POPULATION	Patients aged $\geq 21$ years, but $\leq 75$ years diagnosed with clinically definite, clinically probable, or clinically probable-laboratory supported Amyotrophic Lateral Sclerosis (ALS).
STUDY DESIGN	A phase I/II, open label, single center study designed to assess the safety and tolerability of intramuscular injections of VM202 in patients with ALS. Study enrollment will be staged. Enrollment will be halted after the sixth subject qualifies for treatment. A Data Safety Monitoring Board (DSMB) will conduct a safety evaluation after the first patient treated completes the Day 60 follow-up evaluation and the five other sequentially enrolled subjects complete at least the Day 30 follow-up. Enrollment will be suspended until a formal recommendation to proceed (or not proceed) is made by the DSMB.
NUMBER OF SUBJECTS	18
INCLUSION CRITERIA	

1. Age <math>\geq 21</math> years, but <math>\leq 75</math> years

2. Subjects diagnosed with:

• clinically definite ALS,

• clinically probable ALS, or

• clinically probable-laboratory supported ALS

as specified in the revised El Escorial / Airlie House diagnostic criteria

3. Onset of ALS <math>< 2</math> years at Screening

4. Forced Vital Capacity (FVC) <math>\geq 60\%</math> of predicted

5. Revised Amyotrophic Lateral Sclerosis Functional Rating Scale (ALSFRS-R) <math>\geq 30</math>

6. Not taking riluzole, or on a stable dose for at least thirty days prior to Screening (defined as no noted toxicities)

7. Able and willing to give informed consent

8. If female of childbearing potential, negative urine pregnancy test at Screening and using acceptable method of birth control during the study.

EXCLUSION CRITERIA	

1. Neurological symptom(s) due to vitamin B12 deficiency

- 
2. Requires tracheotomy ventilation or noninvasive ventilation > 16 hours / day
  3. Comorbidities such as Parkinson's disease, schizophrenia, renal failure, or any other severe complication that, in the Investigator's opinion, will compromise the safety of the patient or confound interpretation of the data collected in this study
  4. Other neuromuscular disease
  5. Inflammatory disorder of the blood vessels (inflammatory angiopathy, such as Buerger's disease)
  6. Active infection
  7. Chronic inflammatory disease (e.g., Crohn's disease, rheumatoid arthritis)
  8. Positive HIV or HTLV at Screening
  9. Active Hepatitis B or C as determined by Hepatitis B core antibody (HBcAb), antibody to Hepatitis B surface antigen (IgG and IgM; HBsAb), Hepatitis B surface antigen (HBsAg) and Hepatitis C antibodies (Anti-HCV) at Screening
  10. Subjects with known immunosuppression or currently receiving immunosuppressive drugs, chemotherapy or radiation therapy
  11. Stroke or myocardial infarction within last 3 months
  12. Patients with a recent history (< 5 years) of malignant neoplasm except basal cell carcinoma or squamous cell carcinoma of the skin (if excised and no evidence of recurrence);
  13. Subjects requiring > 81 mg daily of acetylsalicylic acid; subjects may be enrolled if willing/able to switch to ≤ 81 mg daily of acetylsalicylic acid or to another medication
  14. Subjects requiring regular COX-2 inhibitor drug(s) or non-specific COX-1/COX-2 inhibiting drugs, or high dose steroids (excepting inhaled steroids); subjects may be enrolled if willing/able to undergo medication wash-out prior to the first dosing and to refrain from taking these drugs for the duration of the study
  15. Have used an investigational drug within 30 days of Screening
  16. Pregnant or currently lactating
  17. Major psychiatric disorder in past 6 months
  18. Known drug or alcohol dependence or any other factors which will interfere with the study conduct or interpretation of the results or who in the opinion of the Investigator are not suitable to participate.

## SCREENING

Screening will include assessment of study eligibility, a medical history, vital signs, physical exam, concomitant medications, 12 lead EKG, viral screening, FVC, ALSFRS-R, serum chemistry and hematology, and urine pregnancy test (for women of childbearing potential only).

---

**PRE-INJECTION  
EVALUATIONS**

Prior to injections on Day 0, subjects will be assessed using the ALSFRS-R, the Medical Research Council (MRC) scale for muscle strength testing, dynamometry, FVC, and muscle circumference. These tests can be conducted one day before the scheduled injection visit. Immediately before injection on Day 0, the following will be conducted: recording of concomitant medications, vital signs, and blood draw for serum chemistry and hematology, serum HGF and copies of VM202 in whole blood.

**INJECTIONS**

VM202 is delivered in 0.5 mL intramuscular injections of a solution of 0.5 mg VM202 / mL. It will be administered over the course of four visits: Day 0, Day 7, Day 14, and Day 21. As in all previous VM202 studies, final dose of VM202 for each target muscle group is divided and administered 2 weeks apart. However, in order to reduce the injection burden on the ALS patient, injection of the upper limbs will be done on separate visits from injection of the lower limbs. The first eligible subject will begin with the lower limb injection series and will be injected in accordance with the schedule outlined in [Table 1](#). The next sequentially eligible patient will begin with injection of the upper limbs (see [Table 2](#)). Subsequent eligible patients will be treated in an alternating fashion, such that 9 patients will have initiated their VM202 injections in the lower limbs and 9 patients will have initiated their VM202 injections in the upper limbs. ***Please note: Regardless of injection order, all subjects will receive the same final dose of VM202 and the same number of injections per muscle group.***

Table 1. Group 1 Injection Schedule

TARGET AREA	DOSE VM202 (mg) / TARGET MUSCLE, (NUMBER OF INJECTIONS / MUSCLE GROUP / SIDE (R/L))				TOTAL DOSE (TOTAL NUMBER OF INJECTIONS (R + L))
	DAY 0	DAY 7	DAY 14	DAY 21	
Hand					
Abductor pollicis brevis (APB)		1, (2/2)		1, (2/2)	2, (8)
first dorsal interosseous (FDI)		1, (2/2)		1, (2/2)	2, (8)
Upper Arms					
Biceps		4, (8/8)		4, (8/8)	8, (32)
Deltoid		4, (8/8)		4, (8/8)	8, (32)
Lower Arms					
Extensor carpi radialis		1, (2/2)		1, (2/2)	2, (8)
Flexor carpi ulnaris		1, (2/2)		1, (2/2)	2, (8)
Flexor carpi radialis		1, (2/2)		1, (2/2)	2, (8)
Legs					
Quadriceps	10, (20/20)		10, (20/20)		20, (80)
Gastrocnemius	6, (12/12)		6, (12/12)		12, (48)
Tibialis anterior	3, (6/6)		3, (6/6)		6, (24)
Final Dose (# of injections (L + R))	19 (76)	13 (52)	19 (76)	13 (52)	64 (256)

Table 2. Group 2 Injection Schedule

TARGET AREA	DOSE VM202 (mg) / TARGET MUSCLE, (NUMBER OF INJECTIONS / MUSCLE GROUP / SIDE (R/L))				TOTAL DOSE (TOTAL NUMBER OF INJECTIONS (R + L))
	DAY 0	DAY 7	DAY 14	DAY 21	
Hand					
abductor pollicis brevis (APB)	1, (2/2)		1, (2/2)		2, (8)
first dorsal interosseous (FDI)	1, (2/2)		1, (2/2)		2, (8)
Upper Arms					
Biceps	4, (8/8)		4, (8/8)		8, (32)
Deltoid	4, (8/8)		4, (8/8)		8, (32)
Lower Arms					
Extensor carpi radialis	1, (2/2)		1, (2/2)		2, (8)
Flexor carpi ulnaris	1, (2/2)		1, (2/2)		2, (8)
Flexor carpi radialis	1, (2/2)		1, (2/2)		2, (8)
Legs					
Quadriceps		10, (20/20)		10, (20/20)	20, (80)
Gastrocnemius		6, (12/12)		6, (12/12)	12, (48)
Tibialis anterior		3, (6/6)		3, (6/6)	6, (24)
Final Dose (# of injections (L + R))	13 (52)	19 (76)	13 (52)	19 (76)	64 (256)

**OTHER STUDY PROCEDURES / EVALUATIONS**

HGF serum levels will be determined immediately pre-treatment on Day 0, immediately pre-treatment on Day 7, immediately pre-treatment on Day 14, immediately pre-treatment on Day 21, on Day 30, Day 60 and Day 90.

The number of copies of VM202 in whole blood will be determined at Day 0 (pre-injection, and 2 hours [± 1 hour] post last injection), at Day 7 (pre-injection, and 2 hours [± 1 hour] post last injection), at Day 14 (pre-injection, and 2 hours [± 1 hour] post last injection), at Day 21 (pre-injection, and 2 hours [± 1 hour] post last injection), on Day 30, Day 60 and Day 90.

ALSFERS-R, FVC and muscle strength (as determined by using the MRC scale) will be assessed at Day 30, Day 60, Day 90, at 6 months and 9 months. Muscle circumference and dynamometry will be conducted on Day 60, Day 90, at 6 months, and 9 months.

A Data Safety Monitoring Board (DSMB) will monitor patient safety throughout the study.

---

**SCHEDULE OF EXAMINATIONS**

Screening (Day -30 to Day 0)

Day 0

Day 7 ± 1 days

Day 14 ± 1 days

Day 21 ± 1 days

Day 30 ± 3 days

Day 60 ± 3 days

Day 90 ± 7 days

Month 6 ± 1 month

Month 9 ± 1 month

Subjects will be followed up at 12, 18, 24, and 36 months (1 ± month) by phone to assess survival.

**STUDY ENDPOINTS**

The primary study endpoint is to evaluate safety and tolerability of intramuscular injections of VM202 at different injection sites in subjects with ALS. Secondary endpoints include the assessment of the neuroprotective potential of VM202.

**SAFETY**

Adverse events (including serious adverse events, and adverse events leading to treatment discontinuation) throughout the 9 months follow-up will be described according to severity and to their relationship with the study drug and injection procedure. Descriptive statistics will be used to characterize safety parameters.

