### 3.2. STUDY DESIGN

This is a phase I/II, open label, single center study designed to assess the safety and tolerability of intramuscular injections of VM202 in patients with ALS. Subjects with ALS will be screened for study eligibility after giving informed consent.

**Screening.** Using the revised El Escorial / Airlie House diagnostic criteria and medical history, subjects will be confirmed as having ALS < 2 years. If applicable, the subject will be washed out of prohibited medication (see [section 3.4.4](#)). During medication wash-out, screening procedures consisting of assessment of study eligibility, a medical history, vital signs, physical exam, concomitant medications, ALSFRS-R, viral screening, 12 lead EKG, FVC, serum chemistry and hematology, and (urine) pregnancy test (for women of childbearing potential only) will be performed.

All screening assessments should occur within the 30 days prior to Day 0 (day of first injections).

**Injection.** Prior to injections on Day 0, subjects will be assessed using the ALSFRS-R, the Medical Research Council (MRC) scale for muscle strength testing, dynamometry, FVC, and muscle circumference. These tests can be conducted one day before the scheduled injection visit. Immediately before injection on Day 0, the following will be conducted: recording of concomitant medications, vital signs, and blood draw for serum chemistry and hematology, serum HGF and copies of VM202 in whole blood.

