VM202 will be delivered in 0.5 mL intramuscular injections of a solution of 0.5 mg VM202 / mL. It will be administered over the course of four visits: Day 0, Day 7, Day 14, and Day 21. As in all previous VM202 studies, final dose of VM202 for each target muscle group is divided and administered 2 weeks apart. However, in order to reduce the injection burden on the ALS patient, injection of the upper limbs will be done on separate visits from injection of the lower limbs. The first eligible subject will begin with the lower limb injection series and will be injected in accordance with the schedule outlined in [Table 3](#). The next sequentially eligible patient will begin with injection of the upper limbs (see [Table 4](#)). Subsequent eligible patients will be treated in an alternating fashion, such that 9 patients will have initiated their VM202 injections in the lower limbs and 9 patients will have initiated their VM202 injections in the upper limbs. ***Please note: Regardless of injection order, all subjects will receive the same final dose of VM202 and the same number of injections per muscle group.***

---

[REDACTED]

[REDACTED]

Serum chemistry and hematology will be determined on Day 0, Day 30, Day 90 and 9 months.

FVC, ALSFRS-R, and muscle strength (MRC scale) will be assessed at Day 0, Day 30, Day 60, Day 90, at 6 months and 9 months. Muscle circumference and dynamometry will be ascertained on Day 0, Day 60, Day 90, at 6 months, and 9 months.

Concomitant medications and vital signs will be recorded throughout the 9 month follow-up period. Adverse events will be assessed starting on Day 0 throughout the 9 month follow-up period, and injection site reactions will be assessed starting on Day 0 through Day 60. Study enrollment will be staged. Enrollment will be halted after the sixth subject qualifies for treatment. A Data Safety Monitoring Board (DSMB) will conduct a safety evaluation after the first patient treated completes the Day 60 follow-up evaluation and the five other sequentially enrolled subjects complete at least the Day 30 follow-up. Enrollment will be suspended until a formal recommendation to proceed (or not proceed) is made by the DSMB.

The study will be suspended pending DSMB review if any of the following SAEs are attributed to VM202 injections during any time during the study:

- acute anaphylaxis (including erythema, hives, wheezing, stridor or respiratory distress);

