### **3.3. SUBJECT POPULATION**

Eighteen (18) evaluable subjects with ALS meeting the following study entry criteria will be enrolled.

---

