### **5.3. REPORTING/RECORDING OF AEs**

---

Throughout the course of the study, all efforts will be made by the Investigator to remain alert to possible AEs. The first concern will be the safety of the subject, and

---

for providing appropriate medical intervention. The period of observation for collection of AEs starts during the first intramuscular injection procedure (Day 0) until the 9 month follow-up visit. Any AE should be recorded on the appropriate CRF page(s).

---

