### **6.2.1. SAFETY**

Any patient who receives VM202 will be included in the safety analysis population. Adverse events, serious adverse events, and adverse events leading to treatment discontinuation will be summarized using descriptive statistics. Categorical variables will be summarized by the number and percentage of patients in each category. Continuous variables will be summarized using n, mean, SD, median, minimum, and maximum values. No statistical testing will be performed.

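### Adverse events are summarised over nine months with no split by onset, so for common event types clustering around the Day 0 to 21 injections would not show; one added table would fix this cheaply

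*Combined protocol and SAP*

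**What the plan says.** Dosing is short. Section 3.2 says of VM202: "It will be administered over the course of four visits: Day 0, Day 7, Day 14, and Day 21". The last visit has a tolerance of one day, so injections end by about Day 22. There is no comparator: the study is open label, and whatever the injection order, "all subjects will receive the same final dose of VM202 and the same number of injections per muscle group".

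Collection of adverse events is long. Section 5.3 states: "The period of observation for collection of AEs starts during the first intramuscular injection procedure (Day 0) until the 9 month follow-up visit".

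The summary follows the long period. In the synopsis (Safety), adverse events "throughout the 9 months follow-up will be described according to severity and to their relationship with the study drug and injection procedure". Section 6.2.1 says: "Adverse events, serious adverse events, and adverse events leading to treatment discontinuation will be summarized using descriptive statistics". It adds: "Categorical variables will be summarized by the number and percentage of patients in each category". Section 5.2 records the onset date of each event, but neither the synopsis nor Section 6 uses it. No table by time since injection and no rate per unit of follow-up is planned.

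**The concern.** Safety and tolerability of the injections is the primary endpoint. With no control group, the timing of events relative to dosing is one useful piece of internal evidence. A percentage of patients with an event at any time in nine months discards that timing. It also approaches 100% for event types that most patients would have anyway, so a burst of events in the dosing weeks can barely move it. The planned split by relationship to drug and procedure helps, but an unblinded investigator makes that judgement. Section 5.2.1 already builds plausibility of timing into the categories, so timing would enter the report only inside the judgement and would never be shown separately.

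**Working it through.** The plan gives no adverse event rate and no statistical basis for the 18 subjects, so there is no figure to reproduce. The rates below are assumptions, used only to show how the summaries behave.

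**Inputs from the documents.** Injections on Days 0, 7, 14 and 21 (Section 3.2); observation to 9 months (Section 5.3); 18 subjects (Section 3.3). With 9 × 30.44 = 274 days, the 21-day dosing span is 21/274 = 7.7% of follow-up, and Days 0 to 30 are 30/274 = 11%.

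**Any adverse event.** Assume Poisson events at rate r per patient-month, tripled in month 1, which adds 2r expected events.
- Nine months: 1 − exp(−9r) becomes 1 − exp(−11r).
- Month 1: 1 − exp(−r) becomes 1 − exp(−3r).

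| Assumed r | Any event, 9 months | Any event, month 1 |
|---|---|---|
| 0.1 | 59% to 67% | 10% to 26% |
| 0.3 | 93.3% to 96.3% | 25.9% to 59.3% |
| 0.5 | 98.9% to 99.6% | 39% to 78% |

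At r = 0.3, total events in 18 subjects rise from 18 × 2.7 = 48.6 to 18 × 3.3 = 59.4, or 22%. Without a control the reader would see only the second figure of each pair.

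**By how common the event is.** Let b be the background nine-month incidence, T = 274 days and λ = −ln(1 − b)/T, with the rate tripled in Days 0 to 30. Then the nine-month percentage is 1 − exp(−λ(T − 30) − 90λ), and the Day 0 to 30 percentage is 1 − exp(−90λ), against 1 − exp(−30λ) at background.

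| b | 9 months | Excess patients of 18 | Days 0 to 30 | Excess patients of 18 |
|---|---|---|---|---|
| 20% | 20% to 23.8% | 0.7 | 2.4% to 7.1% | 0.8 |
| 60% | 60% to 67.3% | 1.3 | 9.5% to 26.0% | 3.0 |
| 90% | 90% to 94.0% | 0.7 | 22.3% to 53.1% | 5.5 |

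With a fivefold rate, the nine-month percentage rises by factors of 1.37, 1.22 and 1.07 in the three rows, against 4.8, 4.1 and 3.2 in Days 0 to 30. At b = 5% to 20% with a tripled rate, the excess is 0.2 to 0.7 patients over nine months and 0.2 to 0.8 in the early window. The loss is therefore confined to common events.

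**Where to cut.** The last injection can fall on Day 22 (21 + 1) and the Day 30 visit on Day 27 (30 − 3), so a cut at that visit could come 5 days after the last dose. Section 3.2 itself uses a two-week post-dose window, in its suspension trigger for injection-site necrosis. Last injection plus 14 days is nominally Day 35, or 35/30.44 = 1.15 months.

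**What that table would show at r = 0.3.** Early events per patient are 0.3 × 1.15 + 0.6 = 0.945, a rate of 0.945/1.15 = 0.82 per patient-month against 0.30 later. In 18 subjects that is about 17.0 early events and 18 × 0.3 × 7.85 = 42.4 later ones.

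**Ascertainment.** Appendix 1 schedules eight adverse event assessments by Day 30 (Day 0 post-dose; Days 7, 14 and 21 pre- and post-dose; Day 30) and four afterwards (Days 60 and 90, months 6 and 9).

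**The case against.** A reader might infer that the plan reports one undifferentiated nine-month percentage and that a dosing effect would vanish into ALS background. The documents do not support that. Events are split by severity and by relationship to drug and procedure. Section 5.1 keeps changes consistent with natural progression out of the adverse event record. The percentage rule in Section 6.2.1 is general, and no any-event line is named as the safety result.

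Nor is event timing the only evidence independent of causality judgement. Vital signs are taken before and after injection at every dosing visit (4.2.2), laboratory tests on Day 0 and Day 30 (4.2.3), and injection-site checks through Day 60 (4.2.11). The suspension triggers and the scheduled DSMB review of the first six subjects also watch the early period.

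An early-against-late contrast has its own weaknesses. Denser early assessment can raise the early rate by itself. A subject who receives 256 injections will probably have local reactions early. The later period is not free of exposure either: HGF and plasmid copies are sampled to Day 90.

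All of this stands, and it limits the size of the point and shapes the remedy. It does not remove the gap. The relationship and progression calls are both made unblinded. The other early measurements do not replace a time profile of systemic events. Section 6.2.1 names no separate injection-site table, and the triggers and DSMB review govern conduct, not the final summary of all 18 subjects.

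**Conclusion.** A cheap improvement to the primary safety analysis. It is not a flaw that invalidates the analysis. The documents establish short dosing, nine-month summaries, no control, and onset dates that no planned summary uses. On assumed rates, a tripled rate in the first month raises an all-causality nine-month percentage by a factor of only 1.04 (90% background) to 1.21 (5% background). The loss in patient counts matters for common event types and is negligible for uncommon ones. These sizes rest on Poisson events, a constant background and the assumed rate ratios, none of which the documents supply. It would go too far to conclude that an injection-related signal would be missed, because the planned splits and early checks could still reveal one.

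**What to change.** In Section 6.2.1, keep the planned tables and add one descriptive table by onset period within the same subjects:
- **Early:** first injection to 14 days after that subject's last injection.
- **Later:** from then to the 9-month visit or withdrawal.

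For each period give patients with events, number of events and events per patient-month, overall, by severity and by relationship. Show injection-site reactions separately from other adverse events. Patient-time denominators also handle subjects who leave early, who remain in the safety population.

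The table note should say that bias can run either way. ALS progression may raise the later rate; eight scheduled assessments by Day 30 against four afterwards may raise the early rate; and the later period is not fully free of exposure. No test is needed. The periods should be fixed before the data are reviewed, because a cut chosen afterwards in an open-label study would be less credible.

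Cost: one extra table from data already collected, with limited causal interpretation.

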**PHARMACOKINETICS & PHARMACODYNAMICS**

HGF serum levels will be determined immediately pre-treatment on Day 0, immediately pre-treatment on Day 7, immediately pre-treatment on Day 14, immediately pre-treatment on Day 21, on Day 30, Day 60 and Day 90. The number of copies of VM202 in whole blood will be determined at Day 0 (pre-injection, and 2 hours [± 1 hour] post injection), at Day 7 (pre-injection, and 2 hours [± 1 hour] post injection), at Day 14 (pre-injection, and 2 hours [± 1 hour] post injection), at Day 21 (pre-injection, and 2 hours [± 1 hour] post injection), on Day 30, Day 60 and Day 90.

**EFFICACY**

This study is not powered to detect differences in efficacy measures. However, descriptive statistics (N, mean, median, SD, minimum and maximum values, where applicable) of clinically meaningful endpoints will be tabulated. Endpoints will include, but are not limited to the following:

- ALSFRS-R scale
- Muscle circumference
- Forced vital capacity
- Dynamometry (finger pinch, grip strength and extension of lower leg)

- 
- Muscle strength as evaluated by the MRC scale – scoring only of the subset of muscles specifically injected in this study.

---

